Once the infant's withdrawal symptoms have been stabilized with oral morphine and the mother has agreed to participation (signed ICF/RA), infants will be assigned to receive only donor human milk (Co-op donor milk, Medolac Laboratories, Lake Oswego, OR) for a period of 2 weeks. Vitamin supplementation or other nutritional adjustments will be at the discretion of the attending physician.

Infant Finnegan scores will be assessed according to the current NAS protocol. Oral morphine dosing (increases or weaning doses) will be consistent with the current NAS protocol.

Primary outcome:

[figure not shown]
Acceptability (no increase in GI sub-scores compared to historic formula-fed controls) Appropriate growth

See data collection sheet for detailed list of variables.

Statistical analysis:

[figure not shown]
Descriptive statistics will be provided. As this is a pilot study, no inferential statistics will be applied.

Figure 1. Cases of neonatal abstinence syndrome (NAS) in Kentucky (20002012)*

^{*}Data from Kentucky Injury Prevention Research Center, January 2014

Figure 2. Healthcare expenditures (in \$ millions) for treatment of neonatal abstinence syndrome (NAS) in Kentucky (2000-2012)*

2000 2001 2002 2003 2004 2005 2006 2007 2008 2009 2010 2011 2012

Table 1. Modified Finnegan Scoring Tool⁴

System symptoms	Total (frequency)
CNS	
High-pitched cry Continuous high-pitched cry	2 3
Sleeps <1 h after feeding Sleeps <2 h after feeding Sleeps <3 h after feeding	3 2 1
Hyperactive Moro reflex Markedly hyperactive Moro reflex	2 3
Tremors disturbed Mild tremors undisturbed Moderate severe tremors undisturbed	2 3 4
Increased muscle tone	2
Excoriation (specify area)	1
Myoclonic jerks	3
Generalized convulsions	5

^{*}Data from Kentucky Injury Prevention Research Center, January 2014

Metabolic	
Sweating	1
Fever 37.2°C – 38.3°C Fever	1
>38.4°C	2
Frequent yawning >4 x per interval	1
Mottling	1
Vasomotor	
Nasal stuffiness	1
Frequent sneezing >4 x per interval	1
Respiratory	
Nasal flaring	2
Respiratory rate >60/min	1
Respiratory rate >60/min + retractions	2
Gastrointestinal	
Excessive sucking	1
Poor feeding	1
Regurgitation	2
Projective vomiting	3
Loose stools Watery	2
stools	3
GI sub-score range: 0 to 10	
Total score range	0 to 44

REFERENCES

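### Do the two score ranges printed in Table 1 conflict in a way that touches the primary GI outcome?

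*Combined protocol and SAP*

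**What the plan says.** Table 1 (Modified Finnegan Scoring Tool) gives item weights by body system. The gastrointestinal block reads "Excessive sucking 1", "Poor feeding 1", "Regurgitation 2", "Projective vomiting 3", and a stool entry with loose stools at 2 and watery stools at 3. Below it stands "GI sub-score range: 0 to 10", followed by a total range of 0 to 44. Elsewhere the table shows graded signs as alternatives, for example "High-pitched cry Continuous high-pitched cry 2 3". It does not say which GI items exclude one another.

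Under Methods, scoring is referred to the NAS protocol in current use, and under Primary outcome the variables are referred to a data collection sheet. The acceptability part of the primary outcome is that GI sub-scores do not rise relative to formula-fed infants from past records. The end of the Background says that total scores will be compared too. Under Statistical analysis, only descriptive statistics are planned.

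**The concern.** Two maxima printed side by side should follow from one scoring rule. Here they do not, and the natural candidate for the discrepancy is the GI block, where regurgitation and projectile vomiting may be read either as two signs that add or as two grades of one sign. The first reading gives a GI maximum of 10, the second 8.

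The GI sub-score is the subject of the null hypothesis and of the acceptability criterion, and that criterion carries no margin. If enrolled infants were summed under one reading and the historic infants under the other, part of the difference between groups would come from the scoring and not from the milk. The result is meant to inform a randomized trial, so an artefact would carry forward.

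**Working it through.** All inputs are the weights in Table 1.

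**1. The GI range.** Count regurgitation and vomiting separately and take the higher stool grade: sucking 1 + poor feeding 1 + regurgitation 2 + vomiting 3 + watery stools 3 = **10**. The printed GI range is reproduced.

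**2. Items outside the GI block, highest grade of each graded sign.**

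| System | Sum | Maximum |
|---|---|---|
| CNS | cry 3 + sleep 3 + Moro 3 + tremors 4 + tone 2 + excoriation 1 + jerks 3 + convulsions 5 | 24 |
| Metabolic | sweating 1 + fever 2 + yawning 1 + mottling 1 | 5 |
| Vasomotor | stuffiness 1 + sneezing 1 | 2 |
| Respiratory | flaring 2 + rate with retractions 2 | 4 |
| Non-GI | 24 + 5 + 2 + 4 | **35** |

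**3. Totals.**

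| GI reading | GI maximum | Total = 35 + GI |
|---|---|---|
| Regurgitation/vomiting exclusive, stools exclusive | 1+1+3+3 = 8 | 43 |
| One of the two pairs added | 10 | 45 |
| Both pairs added | 12 | 47 |

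The printed 44 appears in no row. It is 1 below the total that goes with GI 10 and 1 above the total that goes with GI 8.

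**4. Could another rule give 10 and 44 together?** Start from 43, with every graded set at its maximum. Summing a set instead adds: cry +2, sleep +3, Moro +2, tremors +5, fever +1, respiratory rate +1, regurgitation/vomiting +2, stools +2. A total of 44 needs exactly +1, so only fever or only respiratory rate is summed, and in both cases GI stays at 8. With GI at 10 the total is at least 45. The two printed figures coincide only if separately listed signs are merged, for instance stuffiness and sneezing counted once: 24 + 5 + 1 + 4 + 10 = 44. That is contrived. The likely explanation is an addition error in the total.

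**5. What the GI ambiguity could do.** A scoring with both regurgitation and projectile vomiting gives 2 + 3 = 5 if they add and 3 if they exclude each other, a gap of 2. If a fraction p of scorings shows both signs, changing the rule moves a group's mean by 2 × p. With p assumed at 10% to 25% (the documents give no figure), that is 0.2 to 0.5 point. It becomes a spurious difference between groups only if one group is summed one way and the other group the other way. Under a common rule the difference between groups reflects how often the signs occurred.

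**6. Where the maxima are used.** Eligibility uses a score threshold of 8. The primary outcome uses observed GI sub-scores. The analysis is descriptive. No criterion, rescaling, percentage of maximum or sample-size calculation uses 10 or 44.

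**The case for a change.** The strongest case for a change is that the documents never state how GI items combine, and the layout does not settle it. Regurgitation and vomiting are on separate lines, but so are the two respiratory-rate entries, the second of which contains the first. With historic controls, no margin and no formal test, any difference in means could be read as the answer, and nothing in the text guarantees that both groups' sub-scores are derived alike. One sentence would close the gap.

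The observation that the rule is unwritten stands, and so does the 1-point slip in the total. The inference of harm does not. Scoring is delegated to an existing NAS protocol that is not reproduced here and may well say which items are exclusive. Nothing in the text indicates that past infants were scored under another rule, and an analyst who builds a GI sub-score from charted items would ordinarily use one formula for everyone. Frequent co-occurrence is also doubtful at the start: enrolled infants must have had scores below 8 for 24 hours, so the two signs together would take 5 of at most 7 points, although later scores could be higher. Finally, with descriptive reporting and no stated summary measure, there is no formal decision rule for a small shift to overturn.

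**Conclusion.** The printed total maximum is off by 1 point under any ordinary reading of Table 1: it should be 45 alongside a GI maximum of 10, or 43 alongside 8. The GI range is not shown to be wrong, since 10 follows from a plain reading. The 2-point gap between 8 and 10 is a separate matter, a scoring convention that this text leaves to the NAS protocol.

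No change to the plan follows. The wrong total is a clerical slip that affects no observed score, eligibility decision or conclusion. The unwritten convention is a detail that analysts fill sensibly by applying one formula to both groups. This rests on two assumptions: that the weights in the extracted table are as printed (they are all legible, though some rows are split), and that donor-milk infants and historic controls are scored under the same convention. If the second failed completely, the artefact would be 0.2 to 0.5 point at the assumed co-occurrence of 10% to 25%, but the documents give no reason to expect that.
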